11.2. Secondary endpoints	10
11.3. Adjudication of endpoints	10
12. Statistics	10
12.1. Sample size estimate.....	10
12.2. Analysis	10
13. Side effects, risks, and disadvantages	11
14. Ethical considerations	11
15. Study organisation	11
15.1. Coordinating centre	11
15.2. Steering committee.....	12
16. Economy.....	12
17. Feasibility	12
18. Publication	13
19. Summary	13

20.	Dansk resume.....	13
	Protocol amendments.....	14
21.	Change in study population, May 2017	14
22.	Change in sample size estimation, June 2018.....	14
23.	References	15

Protocol

Version 06.06.2018 (final)

1. Background

Atrial fibrillation (AF) is common in patients with pacemakers and is associated with an increased risk of thromboembolism (1). Recently, we have shown that treatment with dual chamber pacing (DDD) reduces AF when compared to treatment with a single-lead atrial pacemaker (AAIR) (2), and today, DDD pacing is preferred for patients who require treatment for SSS. Typically, the pacemaker is set at a lower rate of 60 bpm and programmed to increase the heart rate during physical activity (rate-response (RR) function on). Using this setting, AF is observed in 50% of the patients with SSS within the first two years after pacemaker implantation (3). Studies have indicated that the incidence of AF increases with higher proportions of atrial pacing (4). It is not known whether an increased amount of atrial pacing *causes* AF, or simply indicates that patients who require more atrial pacing also have an increased risk of developing AF. Atrial pacing causes an abnormal electrical activation of the atria, which often leads to prolonged atrioventricular (AV) conduction resulting in more frequent ventricular pacing; all factors that have been shown capable of increasing the incidence of AF (5-11). Recent studies have confirmed that atrial overdrive pacing (intended atrial pacing at a higher rate than the intrinsic heart rhythm) does not reduce the incidence of AF and this is not recommendable (12). No other studies have investigated whether a lower pacing rate - and thus a lower proportion of atrial pacing - reduces the incidence of AF. The present randomised trial aims to test the hypothesis that reducing the atrial pacing rate to 40 bpm with the rate-response function off, reduces the incidence of AF when compared to conventional pacemaker programming at a rate of 60 bpm and activated rate-response function in patients with SSS.

2. Hypothesis

Reducing the pacing rate to 40 bpm with the RR function off (DDD-40) significantly reduces the incidence of AF when compared to conventional pacemaker programming at a lower rate of 60 bpm and an activated RR function (DDDR-60) in patients with SSS.

3. Aim

To investigate, in a randomised design, whether reducing the pacing rate to 40 bpm with the rate-response function off reduces the incidence of AF compared to conventional pacemaker programming at a lower pacing rate of 60 bpm and activated rate-response function in patients with SSS.

4. Study design

A Danish, multicentre, randomised study with participation of all Danish pacemaker-implanting centres. Expected inclusion during a period of 2-2½ years, and two years of follow-up.

5. Inclusion criteria

- Sick sinus syndrome with or without AV block and an indication for first-time implantation of a DDD pacemaker: symptomatic sinus pauses (>2 seconds) or bradycardia with or without paroxysmal AF
- Age \geq 18 years
- Patient informed consent

6. Exclusion criteria

- Permanent or persisting (>7 days) AF prior to implantation
- Persistent symptomatic sinus bradycardia and/or chronotropic incompetence where DDD-pacing at a frequency of >40 bpm is indicated (verified with long term ECG monitoring)
- Life expectancy <1 year
- Participation in another interventional research study
- Indication for implantable cardioverter defibrillator (ICD) or cardiac resynchronization therapy (CRT)
- Pregnancy

7. Study course

Patients fulfilling the inclusion criteria will be asked to participate in the study either before the operation or within the first two days after the operation. Randomisation into the two study arms will be internet-based. Randomisation will be stratified for paroxysmal AF and sex documented before pacemaker implantation (bradycardia-tachycardia syndrome). The pacemaker will be programmed into the assigned pacing mode shortly after the implantation, or after randomisation if randomised after implantation. The case report form (CRF) will be internet-based. Patients will be followed-up in the outpatient clinic after 3 months, 12 months, and 24 months. Pacemakers from the following companies may be implanted, as these include home monitoring: Biotronik, Boston Scientific, Medtronic, and St. Jude Medical.

8. Baseline data

- Age
- Sex
- Arrhythmia (SSS with pauses >2 sec without AF/bradycardia-tachycardia syndrome (paroxysmal AF and sinus pauses/bradycardia)/SSS without pauses or AF)
- Symptoms (syncope/presyncope or dizzy spells/palpitations)
- Height and weight
- QRS duration

- Medical treatment, anticoagulation treatment (warfarin, dabigatran, or the like, and ASA)
- Previous PCI or CABG
- Previous acute myocardial infarction
- Claudication (peripheral atherosclerosis)
- Medical treatment (beta-blocker, Angiotensin-converting enzyme inhibitors (ACE-I)/Angiotensin receptor blockers (ARB), diuretics, calcium channel blocker, amiodarone, sotalol, digoxin, class Ic antiarrhythmics)
- Creatinine, Na⁺, and K⁺
- Previous TCI or stroke
- PR interval
- Diabetes mellitus
- NYHA functional class
- Significant heart valve disease or previous heart valve operation
- Hypertension (medically treated)
- Chronic obstructive lung disease (medically treated)
- Heart dimensions measured by echocardiography <3 months prior to implantation (LVEF, LVEDV, LVESV, and LA volume by Simpson's biplane method, and m-mode echocardiography with LA diameter, incl. LVEDD and LVESD)
- Recording of RV electrode position (apical/other) and RA electrode position (auricle/other) during the implantation

A 12-lead ECG of the intrinsic heart rhythm must be recorded prior to the pacemaker implantation and sent to the study secretariat. The ECG will be scanned into the CRF.

9. Follow-up data

All patients will be connected to remote monitoring, which will be followed centrally by a dedicated technician/nurse located at the coordinating centre. If desired, the implantation centres may review data from their patients via remote monitoring. All endpoints via remote monitoring will be validated.

The following data will be collected via remote monitoring:

- Pacemaker settings and values
- Time to first episodes of AF >6 min, >6 hours, and >24 hours, respectively
- Number of AF episodes >6 min, >6 hours, and >24 hours
- Percentage of time in mode switch
- Percentages of atrial- and ventricular pacing

The following data will be collected at pacemaker follow-up after 3 months, 12 months, and 24 months, and at any additional visits and entered to the CRF:

- Has the patient crossed from one study arm to another (date and cause)

- Hospitalisation(s) for AF since last visit (date)
- Direct current (DC) cardioversion or cardioversion using antiarrhythmics (date and type)
- Did the patient developed persistent AF (>7 days) (date)
- Did the patient have a stroke/TCl (date)
- Did the patient have other thromboembolic events (type and date)
- Pacemaker complications since last visit (type and date)

At 12 months follow-up the following supplementary evaluation will be done:

- QOL questionnaire (SF-36), the questionnaire will be mailed to the patient from the study secretariat after approximately 10 months. The patient will be asked to complete the questionnaire, and either bring it at 12 months follow-up, or return it directly to the study secretariat.
- 6-minute walk test (6-MWT)

In cases where patients develop symptoms raising suspicion of chronotropic incompetence, and the responsible physician finds an indication for changing the pacemaker programming from DDD-40 to DDDR-60, the following procedure must be complied with before crossing over: a 24-hour Holter monitoring must be completed (including the patient recording of symptoms) and an exercise test. Subsequently, the pacemaker programming can be changed to DDDR-60. The patient must undergo clinical re-evaluation after one month. If there is a clinical effect of the changed programming the pacemaker should be left in DDDR mode at 60 bpm. If symptoms have not improved, the pacemaker must be reprogrammed to the allocated modus (DDD-40), and the cause of symptoms be determined by other means. This is to minimise unnecessary crossovers.

If pacemaker complications are detected via remote monitoring, the implanting centre will be informed by the study secretariat. In case of AF lasting >24 hours, the implanting centre will be informed via the study secretariat for the purpose of possible DC cardioversion and/or initiation of anticoagulation treatment.

10. Pacemaker programming

11. Intervention group

DDD, lower pacing rate 40 bpm, RR function off, mode-switch active with shift to DVIR/DDIR/VVIR 60 bpm, atrio-ventricular interval (AVI) paced 150 ms and sensed 130 ms with prolongation of AVI by AVI-hysteresis promoting intrinsic conduction to a max AVI of 230 ms, and rate adaptive AVI.

12. Control group

DDDR, lower pacing rate 60 bpm, RR activated (low-moderate), mode-switch active with shift to DVIR/DDIR/VVIR 60 bpm, AVI paced 150 ms, and sensed 130 ms with prolongation of AVI by AVI-hysteresis promoting intrinsic conduction to a maximum AVI of 230 ms, and rate adaptive AVI.

No AF suppression algorithms are used. Change to AAI(R) pacing mode is not allowed. The maximum AVI of 230 ms must not be exceeded.

13. Endpoints

14. Primary endpoint

Time to first episode of AF >6 minutes detected by the pacemaker.

15. Secondary endpoints

- Time to first episode of AF >6 hours detected by the pacemaker
- Time to first episode of AF >24 hours detected by the pacemaker
- Number of AF episodes
- Percentage of time in AF
- Time to persistent AF
- Hospitalisation due to AF
- Time to DC cardioversion or medical conversion for AF
- Time to crossover (reprogramming of the pacing rate)
- Time to stroke, TCI, or thromboembolic event
- Time to death
- QOL
- 6MWT

16. Adjudication of endpoints

Primary endpoint: first episode of AF >6 min is adjudicated documented by electrocardiogram. This will be carried out by an independent group of electrophysiologists or competent pacemaker doctors and will be blinded with regard to randomisation arm.

Secondary endpoints: stroke, TCI, thromboembolic events, and first episode of AF >6 hours and 24 hours will be adjudicated by an independent group of electrophysiologists or competent pacemaker doctors and will be blinded with regard to randomisation. Data from patient files will be collected via the study secretariat.

17. Statistics

18. Sample size estimate

Estimation of the study population size: in the control group detection of AF after two years of follow-up is assumed in 50% of the patients as seen in the DANPACE study. With $\alpha=0.05$, $1-\beta=0.80$, and a two-sided test, 262 patients are needed in each group to detect a reduction of an absolute 12.5% (=relative 25 %) to AF in 37.5% of the patients in the intervention group. Therefore, we are planning inclusion of a total of 540 patients randomised equally into the two groups. Patients will be stratified according to prior AF or atrial flutter.

19. Analysis

The incidence of the primary endpoint will be presented with Kaplan-Meier plots, and the statistical comparison between treatment groups will be estimated using log-rank tests and Cox regression

analysis with calculation of hazard ratios. The following subgroup analyses are planned: effect of the intervention in patients with and without AF prior to pacemaker implantation, effect of the intervention in patients with a baseline PR interval of longer or shorter duration than the median value. The incidence of the secondary endpoints will be presented by Kaplan-Meier plots and compared using log-rank tests, or will be reported as absolute values and percentages, mean value with standard deviation, or median with quartiles, and compared using t-tests provided normally distributed data, or corresponding non-parametric test or χ^2 -test. Multivariate analysis of predictors of the primary endpoint will be done using Cox regression analysis. Besides randomisation we are planning to include in the analysis the following baseline parameters: bradycardia-tachycardia syndrome, age, sex, PR-interval, LA size, LVEF. The predictive value of CHADS₂-VASC-score for the primary endpoint will be evaluated.

20. Side effects, risks, and disadvantages

The implantation implies no additional side effects, risks, complications, or disadvantages compared to standard pacemaker implantation. Potential side effects to the intervention (reduction in pacing rate to 40 bpm) are dizziness, fatigue, and reduced functional capacity. In the event of such symptoms, verified by Holter monitoring and an exercise test to result from a lack of increase in heart rate, the pacemaker may easily be reprogrammed to the conventional setting at 60 bpm. Compared to standard pacemaker follow-up the disadvantages are as follows: slightly prolonged follow-up visits (around 10 minutes longer), and at 12 months follow-up completion of a quality-of-life questionnaire and a 6-MWT.

21. Ethical considerations

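### Two protocol secondary endpoints, the AF episode count and the percentage of time in AF, leave the SAP secondary list without explanation, and the count is absent from the whole SAP

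*Combined protocol and SAP*

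**What the plan says.** **Protocol (version of June 2018).** Section 15 lists 12 secondary endpoints. Two of them describe how much AF a patient has, as opposed to when it first occurs: "Number of AF episodes" and "Percentage of time in AF". Section 9 plans to collect matching data by remote monitoring: "Number of AF episodes >6 min, >6 hours, and >24 hours" and "Percentage of time in mode switch". Section 19 gives general methods for secondary endpoints that are not times to an event: summary by mean or median, "compared using t-tests provided normally distributed data, or corresponding non-parametric test".

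**SAP (version of 2023, which reports inclusion of 540 patients in the past tense).** The secondary list under Outcomes has 10 items. Percentage of time in mode switch stands under Explanatory endpoints, followed by the pacing percentages, two associations between pacing and mode-switch time, and a count of patients having catheter ablation. Table 2 is reserved for primary and secondary outcomes. The planned figures include scatter plots of pacing percentage against mode-switch time.

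**Change records.** The SAP Commentary reports two added safety endpoints and two added subgroup analyses (sex and age). The protocol amendments (sections 30 and 31) deal with the study population, the survival criterion, investigators, funding and sample size.

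**The concern.** An endpoint named in the protocol, with data planned for collection, should either be reported or be withdrawn with a reason. If the SAP is followed as written, the episode count is not reported, and a comparison of AF burden between arms is neither specified nor due in the main results table. A reader who sets the report beside the protocol will find two secondary endpoints gone and cannot tell why. That is the usual setting for a question about selective reporting.

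There is also a loss of content. The AF-occurrence endpoints that remain secondary (AF beyond 6 hours, beyond 24 hours, persistent AF) are each a time to a first event, so none counts recurrences. Patients with earlier paroxysmal AF are eligible and form a randomisation stratum; for them a first recorded episode says little about recurrence.

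For burden, the only uses the SAP spells out are associations with pacing percentage. The protocol Background says it is unknown whether more atrial pacing causes AF or merely marks patients at higher risk. An association cannot separate the two; a comparison by randomised arm bears on it directly.

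**Working it through.** No stated figure of the plan is in dispute; the sample size of 262 per group does not enter. The check is a line-by-line match of the two secondary lists, followed by a search of the rest of the SAP and of both change records.

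**Step 1. Match the lists** (Protocol section 15 against the SAP secondary list).

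| # | Protocol item (abbreviated) | In SAP secondary list? |
|---|---|---|
| 1 | First AF beyond 6 h | yes |
| 2 | First AF beyond 24 h | yes |
| 3 | AF episode count | **no** |
| 4 | Percentage of time in AF | **no** |
| 5 | Persistent AF | yes |
| 6 | AF hospitalisation | yes, worded as a time to event |
| 7 | Cardioversion | yes, shortened wording |
| 8 | Crossover | yes |
| 9 | Stroke, TCI, thromboembolism | yes |
| 10 | Death | yes |
| 11 | Quality of life | yes |
| 12 | Walk test | yes |

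12 − 10 = 2 protocol items have no match, and the SAP adds none to its secondary list.

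**Step 2. Search the rest of the SAP.**

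- *Episode count:* not among the safety or explanatory endpoints, subgroups, planned tables or planned figures. The one explanatory item that is a count concerns patients having ablation, not AF episodes.
- *Percentage of time in AF:* no item of that name. The nearest is mode-switch time, under Explanatory endpoints. It is also the only burden variable that Protocol section 9 collects, so it is the likely counterpart. That is an inference, since the SAP does not state the link.

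Of the two, one is therefore absent altogether and one is apparently relabelled and moved from secondary to explanatory.

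**Step 3. Look for an explanation.** The Commentary discloses 2 safety endpoints + 2 subgroups = 4 changes, all additions. Sections 30 and 31 of the protocol contain no endpoint change. Neither record mentions either endpoint.

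**Step 4. Can the endpoints be restored from planned data?** Section 9 covers the counts at three thresholds and mode-switch time, so no new collection is needed. One limit applies. For AF, the blinded review in section 16 concerns first episodes: the first beyond 6 minutes for the primary endpoint and, for the secondary ones, "first episode of AF >6 hours and 24 hours will be adjudicated by an independent group". Recurrent episodes fall outside it, although section 9 also says "All endpoints via remote monitoring will be validated".

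**The case against.** The strongest case on the other side has four parts.

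- **AF burden is largely kept.** Mode-switch time is the variable the protocol collects, and the SAP lists it as an endpoint in its own right, apart from the association items. This stands: burden is reclassified, not deleted. What remains open is the missing statement that it is the protocol endpoint, and the reason for the lower tier.
- **Absence from Table 2 proves little.** The table list also has no table for safety endpoints, and the SAP names no test for quality of life or the walk test. Protocol section 19 still offers general methods, and the SAP does not say that it supersedes the protocol. This stands in part: the count goes unanalysed only if the SAP is read alone. But the SAP is the document an analyst will follow, and quality of life and the walk test stay secondary and so remain due in Table 2.
- **Secondary analyses are exploratory.** True, and it limits the weight of the point. It also removes any multiplicity argument against restoring the endpoints, and it does not explain their removal.
- **A count is hard to interpret.** One long episode counts once, and recurrences are not adjudicated. These may be good reasons to drop it, but the SAP does not give them.

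A reader might infer a wider pattern of unreported changes from "Hospitalisation due to AF" becoming a time to event and from the added explanatory items. The documents do not support that. Section 9 already collects hospitalisation dates and pacing percentages, section 19 already allows Kaplan-Meier and log-rank methods for secondary endpoints, and added explanatory items take nothing away. Nor does the amount of AF named in the protocol summary settle the matter: the term is undefined and could also cover the 6-hour and 24-hour endpoints.

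**Conclusion.** The point holds for two endpoints and no further. Of 12 protocol secondary endpoints, 10 are kept, 1 is missing from the SAP entirely, and 1 appears to have been renamed and moved to the explanatory tier. Neither change is explained. The reading of mode-switch time as the counterpart of percentage of time in AF is an assumption, though a natural one. If it is wrong, both endpoints are lost.

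This should be corrected, but it does not threaten the main result: the primary endpoint, alpha and sample size are unaffected, and the SAP treats all secondary results as hypothesis-generating.

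Because the SAP was written after inclusion of 540 patients, a reader might infer that the endpoints were removed in the light of results. Nothing in the documents shows that results by arm were known when the SAP was prepared. The supported conclusion is an incomplete record of changes that leaves a planned endpoint unreported.

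**What to change.** Either of two routes would settle it.

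**Restore (preferred).**

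- Put both endpoints back in the SAP secondary (exploratory) list and in Table 2 by randomised arm.
- Use the general methods of Protocol section 19, non-parametric where the data are not normally distributed.
- State that mode-switch time is the measure of percentage of time in AF, if that is so.
- Report the episode count at the three thresholds already collected, and note that recurrent episodes lie outside the blinded adjudication of first episodes.
- A follow-up-time denominator is optional. It has some merit because follow-up ends early at death or withdrawal, but the protocol did not plan it.

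**Or record.** If the removal of the count or the reclassification of burden is intended, say so in the Commentary with the reason and the date.

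**Cost.** SAP wording and additional entries in Table 2, from data already planned for collection. The downside is two more exploratory endpoints (3 + 1 = 4 comparisons if the count is tested at every threshold). The existing statement that secondary results are hypothesis-generating and unadjusted for multiplicity already covers these.

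### No adjusted analysis is specified for the 12-month walk test and SF-36, although relevant baseline covariates are already collected; the planned unadjusted tests are valid but give up some precision

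*Combined protocol and SAP*

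**What the plan says.** **Timing.** Protocol section 9 (Follow-up data): "At 12 months follow-up the following supplementary evaluation will be done", followed by SF-36 and the 6MWT. Neither appears in the baseline list in section 8, so no patient has a baseline value of either measure.

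**Method.** Protocol section 19 (Analysis) has one rule for secondary endpoints that are neither time-to-event nor categorical: they are "compared using t-tests provided normally distributed data, or corresponding non-parametric test". No covariates are mentioned.

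**SAP.** The Outcomes section lists quality of life and the walk test as secondary endpoints. Statistical principles describes covariate models, but these are Cox models for the primary outcome. The same holds for the list in protocol section 19 ("bradycardia-tachycardia syndrome, age, sex, PR-interval, LA size, LVEF"), which serves the analysis of predictors of the primary endpoint. Nothing in the SAP replaces the section 19 rule for the two 12-month measures.

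**What is collected.** Section 8 includes age, sex, "Height and weight", "NYHA functional class" and medically treated obstructive lung disease. The SAP names sex and previous AF/AFL as the stratification factors.

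**What the measures bear on.** Section 20 states that potential side effects of the 40 bpm rate "are dizziness, fatigue, and reduced functional capacity".

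**The concern.** A continuous outcome measured once can still be adjusted for other baseline variables, even without its own baseline value. Age, sex, body size, functional class and lung disease plausibly relate to walking distance and to physical quality of life. A t-test or rank test ignores them, and it also ignores the two factors on which randomisation was stratified.

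If the 40 bpm setting reduces AF, the next question is whether that comes at a functional cost. NYHA class is not among the follow-up items, so 6MWT and SF-36 are the only planned scale measures of function and quality of life after randomisation. A wider interval than necessary makes such a cost harder to show and harder to exclude.

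There is a second, smaller gap. The SAP promises a 95% CI with every estimate. If the data are judged non-normal and a rank test is used alone, it supplies no mean difference and no interval.

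**Working it through.** **1. The plan's own figure.** The only sample size in the documents concerns the primary endpoint: 262 per group for 50% versus 37.5%, two-sided α = 0.05, power 0.80 (protocol section 18; SAP, Sample size calculation).

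- Uncorrected: n = [1.960·√(2·0.4375·0.5625) + 0.842·√(0.25 + 0.2344)]² / 0.125² ≈ 246.1, rounded up to 247.
- With continuity correction: (246.1/4)·[1 + √(1 + 4/(246.1·0.125))]² ≈ 261.8, rounded up to 262.

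The stated 262 is reproduced and is unaffected by this point. No SD, target difference or power is given for 6MWT or SF-36.

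**2. Inputs.** 540 patients randomised 1:1 give 270 per arm. Results are in units of the outcome SD because the documents give no SD. R² is the share of outcome variance explained by the seven covariates proposed under the fix. It is not in the documents, so a range of 0.05 to 0.30 is assumed.

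**3. Unadjusted comparison.**

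- SE = √(2/270) = 0.0861 SD.
- 95% CI half-width = 1.96 × 0.0861 = 0.169 SD.
- Difference detectable with 80% power = (1.960 + 0.842) × 0.0861 = 0.241 SD.
- Power for a true difference of 0.2 SD (illustrative) = Φ(0.2/0.0861 − 1.96) = 64%.

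**4. Adjusted comparison.** The SE is multiplied by √(1 − R²). The equivalent gain in sample size is 1/(1 − R²) − 1.

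| Assumed R² | SE ratio | CI narrower by | Half-width (SD) | Detectable difference (SD) | Power for 0.2 SD | Equivalent extra patients |
|---|---|---|---|---|---|---|
| 0 | 1 | – | 0.169 | 0.241 | 64% | – |
| 0.05 | 0.975 | 2.5% | 0.164 | 0.235 | 66% | 5% |
| 0.10 | 0.949 | 5.1% | 0.160 | 0.229 | 69% | 11% |
| 0.20 | 0.894 | 10.6% | 0.151 | 0.216 | 74% | 25% |
| 0.30 | 0.837 | 16.3% | 0.141 | 0.202 | 79% | 43% |

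**5. Two checks on the table.**

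- Missing measurements: if 20% were missing (assumed; 216 per arm), the unadjusted detectable difference would be 0.270 SD. The relative gains would be unchanged.
- Cost of estimating coefficients: seven covariate terms in 540 patients inflate the variance by roughly 7/540 = 1.3%, or about 0.6% of the SE. This matters only in the R² = 0.05 row.

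**The case against.** The strongest reply is that this is a preference for efficiency and not an error. In a randomised trial the t-test and the rank test are valid without covariates. Both endpoints are secondary, the SAP calls secondary analyses exploratory, and no power is claimed for them. All of that stands, and it limits the weight of the point. It does not remove the gain: where no confirmatory test is intended, the estimate and its interval are the result.

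Several stronger readings are tempting, and the documents do not support them.

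- **That strong predictors are being ignored.** No correlation or R² is given for either measure. The predictors one would expect to be strongest, the patient's own baseline 6MWT and SF-36, are not collected. The gain is assumed and may be small, particularly for SF-36.
- **That the comparison is biased.** It is not. Leaving out prognostic stratification factors costs precision and, if anything, makes the unadjusted test slightly conservative.
- **That functional loss is an expected harm.** Section 20 calls these effects potential.
- **That nothing else captures intolerance of the setting.** Time to crossover is a secondary endpoint, with a planned figure showing reasons, and syncope or near-syncope is a safety endpoint. They record related intolerance only as events, so the two 12-month measures remain the only scales.
- **That every covariate is recorded before randomisation.** Section 8 does not say so for each item, and section 7 allows inclusion up to two days after the operation. The fix has to state the timing.

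It is also fair to ask what a linear model does with skewed scores or missing covariates. The fix covers both.

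**Conclusion.** The point holds as a low-cost improvement, not as a defect that threatens a conclusion. No adjusted analysis of the 12-month 6MWT or SF-36 is specified in either document, while relevant covariates and both stratification factors are available.

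Over an assumed R² of 0.05 to 0.30, adjustment narrows the interval by about 2.5% to 16% and lowers the detectable difference from 0.241 SD to between 0.235 and 0.202 SD. Where in that range the trial would fall cannot be told from the documents, and it need not be the same for the two measures. The calculation rests on 270 analysed patients per arm, a normal approximation and a linear relation between covariates and outcome. The primary endpoint and its sample size are untouched.

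**What to change.** Add a short paragraph to the SAP, settled before outcomes are compared by arm:

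- Analyse 12-month 6MWT and each reported SF-36 score by linear regression on arm, sex, previous AF/AFL, age, height, weight, NYHA class and treated lung disease.
- Use baseline values from before the assigned programming starts.
- Report the adjusted mean difference with 95% CI, using robust or bootstrap standard errors if scores are skewed.
- Handle missing covariates by the SAP's existing missing-data rule.
- Keep the unadjusted t-test or rank test as a secondary result.

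Other recorded items such as LVEF, claudication or valve disease could be added, but the list should stay short and be fixed in advance so that covariates are not chosen after the results are seen.

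Cost: SAP wording and a few lines of analysis code. No new data, visits or procedures are needed.
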